
credentialed Qualtrics links provided to them by the study staff. Our study staff is experienced in implementing Qualtrics surveys remotely in prior studies and has extensive experience providing brief intervention for caffeine reduction using the manual-only approach. These data will support feasibility and initial efficacy of future randomized controlled trials in populations experiencing specific caffeine-related problems.

2. Objectives (include all primary and secondary objectives)

Primary objective. Determine to what extent participants will engage with a remote caffeine reduction intervention for caffeine-related problems and find it acceptable.

Secondary objective (a). Determine to what extent participants are successfully able to reduce their caffeine consumption following the remote intervention.

Secondary objective (b). Determine to what extent participants report improvement in common caffeine-related problems (e.g., insomnia, anxiety, gastrointestinal distress) following the remote intervention.

Secondary objective (c). Determine whether participants randomized to the immediate intervention group (at 7-weeks post enrollment and post-treatment) show greater caffeine reductions or greater improvements in caffeine-related problems relative to the delayed treatment group at 7-weeks post-enrollment (prior to delayed treatment). This randomization will allow us to compare the initial efficacy of our intervention with caffeine reductions that may occur spontaneously over the same duration.

3. Background (briefly describe pre-clinical and clinical data, current experience with procedures, drug or device, and any other relevant information to justify the research)

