Community Observer. During the screening or treatment visit, participants will be asked to provide the name and contact information (phone number and email address; email will be the preferred method of contact) for a family member, friend, roommate, or significant other for the purposes of online surveys about their caffeine use. The participant will be asked to confirm with their observer that the study team has permission to contact them. The observer will be contacted twice to complete a brief online survey regarding the participants' caffeine use. The first contact will occur soon after the participant has the *Treatment* visit. The second contact will occur near the time of the participant's *Week 7 follow-up* visit.

Treatment Televisit. Participants determined to be eligible following the screening televisit will be scheduled to complete the treatment televisit shortly after screening. For the immediate treatment group, the treatment the *Treatment* visit will generally occur within one week of the screening televisit. The delayed treatment group will have their *Treatment* visit scheduled for a date approximately 7 weeks after screening. During the *Treatment* televisit, study staff will provide the participants with a digital copy of the caffeine reduction treatment manual used in prior studies (Evatt et al., 2016; Sweeney et al., 2019). As in prior research (Sweeney et al., 2019), study staff will give a brief (i.e., generally less than five minutes) description of the manual and instructions on how to gradually reduce their caffeine consumption over a period of six weeks. Participants will also complete assessments to determine their caffeine consumption and cigarette use over the past 7 days as outlined in Table 1. Participants will also be provided with information about their follow-up visits and how to complete weekly surveys.

Weekly Surveys. At seven days following the treatment televisit, participants will receive a request to complete a survey via Qualtrics link sent via email/text. The survey will consist of standard assessments of anxiety, depressed mood, sleep problems, gastrointestinal problems, past week caffeine/cigarette intake, and problems related to caffeine as outlined in Table 1. They will receive a request to complete the same survey once per week (weeks 1-6) until the Week 7 follow-up televisit.

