Week 7 Follow-up Televisit. At approximately 7 weeks after the treatment televisit, participants will complete a follow-up televisit at which they will complete the same measures as previously administered to assess anxiety, depressed mood, sleep problems, gastrointestinal problems, past week caffeine/cigarette use, and caffeine-related problems as outlined in Table 1. Participants will also complete a treatment acceptability survey.

Week 14 Follow-up Televisit. Finally, participants will complete a follow-up visit approximately 14 weeks after the treatment televisit. They will complete all the same assessments as the Week 7 televisit, except they will not repeat the treatment acceptability survey.

Table 1. Study measures according to visit

	Preliminary Online Screening	Screening Televisit	Treatment Televisit	Weekly Surveys (Weeks 1-6)	Week 7 Televisit	Week 14 Televisit
Basic screening questions/demographics ¹	X					
Typical Week Caffeine Survey	X					
AUDIT-C ²	X					
DAST-10 ³	X					
PROMIS-Anxiety-8a ⁴	X			X	X	X
PROMIS-SleepDisturbance-8a ⁴	X			X	X	X
PROMIS-GIDiarrhea-6a ⁴	X			X	X	X
PROMIS-GIReflux-13a1.0 ⁴	X			X	X	X
PROMIS-Depression-8a ⁴	X			X	X	X
Consent Quiz ¹		X				
Medical History Survey ¹		X				
Drug Use History Matrix ¹		X				
Caffeine Timeline Follow-back ¹		X	X		X	X
Past 7 Days Caffeine Survey ¹		X	X	X	X	X
Past 7 Days Cigarette Survey (smokers only) ¹		X	X	X	X	X
Caffeine Problems Survey ¹		X				
Caffeine Use Disorder Questionnaire ¹		X			X	X
Caffeine Use Disorder Interview ¹		X				
GAD-7 ⁵		X			X	X
PSQ-I ⁶		X			X	X
Insomnia Severity Index ⁷		X			X	X
GSRS ⁸		X			X	X
Treatment Acceptability Survey/Interview ¹					X	
Observer Rating Survey (Completed by Community Observer) ¹				X		X

Note. Detailed descriptions of all measures are appended to the present IRB application in the "Measures" document. ¹Study team-generated measure/survey based on prior research (e.g., Sweeney et al. 2019, 2020). ²Alcohol Use Disorders Identification Test-C, Bush et al., 1998. ³Drug Abuse Screening Test, Skinner 1982. ⁴Patient-Reported Outcomes Measurement Information System, Cella et al., 2010, Rothrock et al., 2010. ⁵Generalized Anxiety Disorder-7, Spitzer et al., 2006. ⁶Pittsburgh Sleep Quality Index, Buysse et al., 1989. ⁷Bastien et al., 2001. ⁸Gastrointestinal Symptom Rating Scale, Svedlund et al., 1988.

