5. Any medical condition that, in the opinion of the investigators, may interfere with or preclude completion of the study

6. Drugs/ Substances/ Devices

- a. The rationale for choosing the drug and dose or for choosing the device to be used.

There are no proposed drugs or devices in the proposed research study.

- b. Justification and safety information if FDA approved drugs will be administered for non-FDA approved indications or if doses or routes of administration or participant populations are changed.

N/A

- c. Justification and safety information if non-FDA approved drugs without an IND will be administered.

N/A

7. Study Statistics

- a. Primary outcome variable.

To determine to what extent participants will engage with a remote caffeine reduction intervention for caffeine-related problems and find it acceptable (*Primary objective*), we will calculate the percentage of completed assessments for each televisit (Treatment, 7 Week Follow-Up, 14 Week Follow-Up) among eligible participants, as well as self-reported agreement with the items on the treatment acceptability survey completed at the 7 Week Follow-Up televisit (e.g., “I read all or most of the Guide to Caffeine Reduction and Cessation,” “Overall, the guide was helpful during my attempt to reduce or quit caffeine.”)

- b. Secondary outcome variables.

To determine to what extent participants are successfully able to reduce their caffeine consumption following the remote intervention (*Secondary objective (a)*), we will assess caffeine consumption as determined by the caffeine surveys at 7-and 14-week post-treatment follow-ups and compare this with consumption at the screening and treatment televisits.

To determine to what extent participants report improvement in common caffeine-related problems (e.g., insomnia, anxiety, gastrointestinal distress) following the remote intervention (*Secondary objective (b)*), we will assess caffeine related problems, anxiety, sleep problems, and gastrointestinal distress via standardized measures (see Table 1) at 7 and 14 weeks post treatment follow-ups and compare this with scores on these assessments at the screening and treatment televisits.

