To determine whether participants randomized to the immediate intervention group show greater caffeine reductions or greater improvements in caffeine-related problems (*Secondary objective (c)*) at the 7-week follow-up relative to the delayed treatment group over the same time-period, we will compare all of the secondary outcome variables described above between the two treatment groups to compare our intervention relative to spontaneous reduction that may occur with the passage of time.

c. Statistical plan including sample size justification and interim data analysis.

Because the primary purpose of this study is to collect pilot and feasibility data rather than determine efficacy via randomized controlled trial, the statistical analysis will be primarily descriptive. Primary outcomes will be reported as the proportion of completed televisits among eligible participants as well as the mean and standard deviation agreement (visual analog scale) with items on the treatment acceptability survey. With respect to secondary outcomes, means and standard deviations for the standardized assessments in Table 1 will be calculated for screening, treatment, 7 Week Follow-Up and 14-Week Follow-Up visits, and we will also visually inspect individual subject data. With respect to comparisons between the immediate and delayed intervention group, we will use a mixed effects regression model with between-subjects factors of group, a within subjects factor of time, and a group x time interaction term. A power analysis indicates that with two groups, four measurements, an alpha of .05, a desired power of .95, correlation among repeated measures of .5, and conservatively estimating a small effect (e.g., partial eta squared = .02), a sample size of 100 will be sufficient to detect a treatment effect. Further, we will calculate Cohen's *d* and partial eta squared effect sizes using means and standard deviations for pre-and post-treatment for all secondary outcomes. These effect size calculations will be used to determine the necessary sample size for any future large-scale randomized controlled trials to assess clinical effects in different treatment populations. The desired sample size of 100 is also based on our laboratory's proven participant capacity for prior randomized clinical trials and long-term human laboratory studies (e.g., Evatt et al., 2016; Sweeney et al., 2017, Sweeney et al., 2019).

d. Early stopping rules.

8. Risks

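### The delayed group has no symptom or caffeine-problem measure scheduled before its treatment starts at about week 7, so the symptom half of secondary objective (c) has no untreated comparison value

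*Combined protocol and SAP*

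**What the plan says.** Section 2 defines secondary objective (c) as a randomized comparison that includes "greater improvements in caffeine-related problems relative to the delayed treatment group at 7-weeks post-enrollment (prior to delayed treatment"). Section 7.b repeats the aim: "we will compare all of the secondary outcome variables described above between the two treatment groups". The variables it refers to are caffeine consumption, caffeine-related problems, anxiety, sleep problems and gastrointestinal distress.

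Under section 4.a (Treatment Televisit), the delayed group has this "visit scheduled for a date approximately 7 weeks after screening". The assessments listed for it are narrow: "Participants will also complete assessments to determine their caffeine consumption and cigarette use over the past 7 days as outlined in Table 1". In "Table 1. Study measures according to visit", the Treatment column holds only the Caffeine Timeline Follow-back, the Past 7 Days Caffeine Survey and the Past 7 Days Cigarette Survey.

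The analysis sections assume more. For objective (b), section 7.b will "compare this with scores on these assessments at the screening and treatment televisits". Section 7.c states that "means and standard deviations for the standardized assessments in Table 1 will be calculated for screening, treatment, 7 Week Follow-Up and 14-Week Follow-Up visits".

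**The concern.** A delayed-treatment arm serves as a control only if its outcomes are measured at the end of the wait, before treatment. Here the wait ends at the Treatment televisit, and no symptom outcome is scheduled there.

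The symptom half of objective (c) depends on this value. Section 1 says that the group's previous in-person trials did not measure these symptoms before and after reduction, so symptom change is the new question. Section 7.c will use the resulting effect sizes to size later trials. Without an untreated value, those effects also contain spontaneous change and regression to the mean, in a sample selected for reporting a caffeine-related problem.

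Objective (b) suffers as well. The delayed group's only pre-treatment symptom score is at least about 7 weeks old when treatment starts, so its pre-post change mixes waiting time with treatment.

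**Working it through.** **Inputs.** From section 4.a: the Treatment televisit is within about 1 week of screening (immediate) or at about 7 weeks (delayed). Weekly surveys start 7 days after it, and the two follow-ups come about 7 and 14 weeks after it. Table 1 gives the measures at each visit. Section 4.c supports the timeline, giving total durations of about 15 and 21 weeks.

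**Step 1: count the Treatment column.** The symptom or problem measures that Table 1 repeats over time are five PROMIS forms (anxiety, sleep disturbance, diarrhea, reflux, depression), GAD-7, the Pittsburgh sleep index, the Insomnia Severity Index, GSRS and the Caffeine Use Disorder Questionnaire: 5 + 5 = 10. Marked at Treatment: 0 of 10.

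**Step 2: place the visits on weeks since screening.** With Treatment at week t, weekly surveys fall at t+1 to t+6 and follow-ups at t+7 and t+14. Take t = 1 (immediate) and t = 7 (delayed).

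| Measure | Immediate | Delayed |
|---|---|---|
| GAD-7, Pittsburgh sleep index, Insomnia Severity Index, GSRS, Caffeine Use Disorder Questionnaire | 0, 8, 15 | 0, 14, 21 |
| Five PROMIS forms | preliminary screening, 2–8, 15 | preliminary screening, 8–14, 21 |
| Caffeine Problems Survey | 0 | 0 |
| Caffeine Timeline Follow-back | 0, 1, 8, 15 | **0, 7, 14, 21** |
| Past 7 Days Caffeine Survey | 0–8, 15 (weekly) | **0, 7, 8–14, 21** |

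Only the two caffeine-intake measures have an untreated value at week 7 in the delayed group. Every symptom value after baseline in that group falls after treatment has started.

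**Step 3: consequence for (c).** The contrast needed is

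(immediate, Week 7 follow-up − baseline) − (delayed, week 7 untreated − baseline).

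For all 10 measures the third term is missing for every delayed participant by design. The mixed model in section 7.c cannot supply it. If visits are aligned by name, Week 7 in both groups is after treatment. If they are aligned by calendar, the nearest delayed PROMIS value is about week 8, one week into reduction, and the other five measures have nothing until about week 14.

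**Step 4: consequence for (b).** The interval from last pre-treatment score to Week 7 follow-up is 8 − 0 = 8 weeks (immediate) and 14 − 0 = 14 weeks (delayed). For PROMIS these are minimum values, because the baseline is taken at the online pre-screen and no gap to the screening televisit is given.

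**Step 5: the plan's power figure, for context.** Section 7.c states N = 100 for power .95 with 2 groups, 4 measurements, correlation .5 and partial eta squared .02. For the group × time interaction, f² = .02/.98 = 0.0204, λ = f²·N·m/(1 − ρ), df1 = m − 1 and df2 = (N − 2)(m − 1).

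- m = 4, N = 100: λ = 0.0204 × 100 × 4/0.5 = 16.3 and power is 0.936, close to the stated .95. Power of .95 needs N = 108, or N = 98 if f = 0.143 is rounded to 0.15.
- The controlled contrast in (c) uses two time points per group. With m = 2, λ = 8.2 and power at N = 100 is 0.81; power of .95 needs N = 162.

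This applies once the week-7 value is collected. Until then the symptom contrast cannot be estimated at any N.

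**Step 6: two smaller mismatches.** Section 4.a says the weekly survey covers "past week caffeine/cigarette intake, and problems related to caffeine as outlined in Table 1", but the weekly column contains no caffeine-problem measure. The Caffeine Problems Survey appears only at screening, so it cannot show change in either group.

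**The case against.** The strongest reply is that this is an inconsistency rather than a decision to omit control data: sections 7.b and 7.c presuppose symptom scores at the treatment visit, so the team may intend to collect them. That reading is plausible. But staff work from the visit description and Table 1, and both leave the measures out, so the passages must be reconciled before data are lost.

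Table 1 is also not fully reliable. The Observer Rating Survey is marked under the weekly surveys and Week 14, whereas the text places it near Treatment and near Week 7. That calls for care with individual cells, but the symptom rows show no such shift, and the Treatment Televisit text independently lists only caffeine and cigarette use. The appended Measures document was not available.

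Three narrower points stand in part. PROMIS-Depression is not among the outcome domains named in section 7.b; without it the count is 0 of 9. The Caffeine Problems Survey is never named as a change outcome and may only characterise participants at entry, so that point is minor. Finally, this is a mainly descriptive pilot with a feasibility primary objective, which limits the damage to part of (c) and the interpretation of (b). It does not rescue a comparison that the protocol says it will make.

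**Conclusion.** The concern holds. As scheduled, 0 of 10 repeated symptom or problem measures (0 of 9 without PROMIS-Depression) are taken at the delayed group's untreated 7-week point, and the symptom half of objective (c) cannot be estimated. Pre-post symptom change under (b) covers about 14 weeks in the delayed group and about 8 in the immediate group.

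What is missing is the untreated 7-week endpoint. Baseline symptom scores exist in both groups, and caffeine intake has its week-7 control values on two measures. The conclusion assumes that Table 1 and the Treatment Televisit text are what staff will follow, and that visits fall near their nominal weeks. It does not depend on the sample-size calculation. The gap should be closed before delayed participants reach their Treatment visit, because uncollected scores cannot be recovered.

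**What to change.** 1. In Table 1 and the Treatment Televisit text, add the five PROMIS forms, GAD-7, the Pittsburgh sleep index, the Insomnia Severity Index, GSRS and the Caffeine Use Disorder Questionnaire to the Treatment televisit, completed before the manual is given. This is essential for the delayed group and preferable for both.
2. In sections 7.b and 7.c, name the delayed group's Treatment-visit score as its 7-week control value for (c) and its pre-treatment value for (b). Define the levels of the time factor so that the contrast compares treated with untreated participants.
3. Either repeat the Caffeine Problems Survey at Treatment, Week 7 and Week 14, or state that it is not a change outcome. Reconcile the weekly-survey text with the weekly column.

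The cost is a protocol amendment, a consent amendment if the consent describes visit content (those pages were not available), and added questionnaire time at one televisit. The Week 7 televisit already carries the same battery plus the acceptability survey and is expected to take under 30 minutes. No extra visit or participants are needed.

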There will be no anticipated disruption to any ongoing treatment or routine care.

- f. Justification for inclusion of a placebo or non-treatment group.

There will be no anticipated placebo or non-treatment group. These are pilot or preliminary data that may support a future randomized trial which would have a separate IRB approval.

- g. Definition of treatment failure or participant removal criteria.

Participants who are not eligible or who are noncompliant with study tasks will be removed from the study early. There are no other early stopping rules in the study.

- h. Description of what happens to participants receiving therapy when study ends or if a participant's participation in the study ends prematurely.

The intervention consists solely of the treatment manual and brief instructions provided at the treatment televisit, and is not accompanied by any ongoing therapy (Sweeney et al., 2019). All participants who complete the treatment televisit will be able to keep their copy of the treatment manual.

5. Inclusion/Exclusion Criteria

Inclusion Criteria

1. Between 18-75 years old
2. Reside in the United States
3. Read, write, and speak English fluently
4. Able to access a video camera on a smartphone, tablet, or other computer
5. Able to receive text messages or emails (or both)
6. Consume greater than or equal to 200 mg caffeine per day in a typical week
7. Indicate a problem that is caused or worsened by caffeine from among the following options: sleep problems, anxiety or nervousness, frequent urination, heartburn or other digestive issues, feel dependent on or addicted to caffeine

8. Interested in getting help to gradually reduce or eliminate caffeine consumption as part of a research study

Exclusion Criteria

1. Evidence of significant depressive symptoms assessed via PROMIS-Depression-8a and medical history
2. Evidence of problematic alcohol use assessed via the AUDIT-C and medical/substance use history
3. Evidence of problematic substance use other than alcohol, nicotine, or caffeine assessed via the DAST-10 and medical/substance use history
4. Evidence of a significant psychiatric disorder, presentation of acute psychiatric symptoms, or any other mental illness that, in the opinion of the investigators, may complicate participation in the study. [Anxiety and sleep disorders are not anticipated to interfere with study participation and will not generally be exclusionary]

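### No caffeine-problem or symptom measure is scheduled at the delayed group's untreated 7-week visit, so objective (c) cannot be assessed for caffeine-related problems

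*Combined protocol and SAP*

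**What the plan says.** Section 2, objective (c), sets the control value: the delayed group at seven weeks after enrolment, before its treatment. It covers both caffeine reduction and improvement in caffeine-related problems. Section 7.b extends the comparison to all the secondary outcomes. Those include the ones for objective (b): "we will assess caffeine related problems, anxiety, sleep problems, and gastrointestinal distress via standardized measures (see Table 1) at 7 and 14 weeks" after treatment, to be compared with scores at both the screening and the treatment televisits. Section 7.c plans means and standard deviations of the Table 1 assessments at screening, treatment, Week 7 and Week 14.

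Section 4.a places the delayed group's Treatment televisit about seven weeks after screening. The assessments it describes for that visit are caffeine consumption and cigarette use.

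For the weekly surveys, section 4.a lists anxiety, mood, sleep and gastrointestinal scales together with "past week caffeine/cigarette intake, and problems related to caffeine as outlined in Table 1". For Week 7 it lists the same domains with "past week caffeine/cigarette use, and caffeine-related problems as outlined in Table 1". For Week 14 it says: "They will complete all the same assessments as the Week 7 televisit", apart from the acceptability survey. Table 1 marks the "Caffeine Problems Survey" once, under the screening televisit.

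**The concern.** The delayed group is in the design to show what happens without treatment over the same period. That needs a score on each compared outcome just before the delayed group receives the manual. If the schedule collects only intake at that visit, the promised comparison on anxiety, sleep, gastrointestinal symptoms and caffeine-specific problems has a treated arm and no untreated arm. A score not taken before the manual is given cannot be obtained later.

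The second matter is smaller. The text promises weekly data on caffeine problems and points to Table 1 for them, and Table 1 does not contain them. The plan also never says which instrument defines caffeine-related problems, so staff and analyst could each choose differently.

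**Working it through.** No figure is in dispute. The check sets the schedule against the comparisons it has to support.

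**Step 1. Which visit is the delayed group's 7-week point?** Section 4.a puts its Treatment televisit about 7 weeks after screening. The durations in section 4.c agree: about 21 weeks in total, less 14 weeks from treatment to the last visit, leaves 21 − 14 = 7 weeks. For the immediate group, 15 − 14 = 1 week. The visit called Week 7 is counted from treatment, so in the delayed group it falls about 7 + 7 = 14 weeks after screening, when that group has been treated. The weekly surveys also start after treatment (about week 8 after screening in the delayed group), so they give nothing during the waiting period.

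**Step 2. What does Table 1 mark?**

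| Measure | Online screen | Screening | Treatment | Weekly | Week 7 | Week 14 | Televisits marked |
|---|---|---|---|---|---|---|---|
| Past 7 Days caffeine and cigarette surveys | – | X | X | X | X | X | 4 of 4 |
| Caffeine Timeline Follow-back | – | X | X | – | X | X | 4 of 4 |
| Caffeine Use Disorder Questionnaire, GAD-7, PSQ-I, Insomnia Severity Index, GSRS | – | X | – | – | X | X | 3 of 4 |
| Five PROMIS forms | X | – | – | X | X | X | 2 of 4 |
| Caffeine Problems Survey | – | X | – | – | – | – | 1 of 4 |

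Of the 5 + 5 = 10 repeated problem or symptom scales, 0 are marked at Treatment. The section 4.a text for that visit agrees with the table.

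**Step 3. What can be computed?**

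- Objective (c), caffeine intake: yes. Intake is measured at screening, at Treatment (the delayed group's untreated value) and at Week 7 (the immediate group's treated value).
- Objective (c), caffeine-related problems: no. The delayed group's cell at 7 weeks is empty for every participant by design, so this is not ordinary missing data that a mixed model can handle. The model in section 7.c could still be fitted to screening, Week 7 and Week 14 and would return a group-by-time term. Both groups are already treated at the last two of those visits, so the term would compare treated with treated.
- Objective (b), screening to Weeks 7 and 14: yes, from the five questionnaires in the third row. The PROMIS forms can be compared with the online screen.
- Objective (b), treatment televisit as baseline: no, for any problem scale.
- Weekly caffeine-specific problems: no instrument is marked. The weekly column holds only PROMIS forms and intake surveys for participants.

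**Step 4. Side check on the power statement.** Section 7.c assumes four measurements, which only the intake measures have. With f² = 0.02/0.98 = 0.0204 and λ = f²·N·m/(1 − ρ), N = 100, ρ = 0.5 and m = 4 give λ = 16.3 and power 0.936 for the group-by-time test, close to the stated .95. With m = 3, λ = 12.2 and power is 0.885. This drop is not the size of the problem, because the measurement that is lost is the control value itself.

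**The case against.** The strongest reply is that the plan is well supplied with follow-up measures. Objective (b) gives insomnia, anxiety and gastrointestinal distress as its examples, and each has a scale at screening, Week 7 and Week 14. The "Caffeine Problems Survey" is never named as an outcome. It is generated by the study team, whereas section 7.b speaks of standardised measures, and a survey given only at screening fits a role in checking eligibility. The Caffeine Use Disorder Questionnaire recurs at Weeks 7 and 14 and can satisfy the text for those visits. No stated analysis uses the weekly problem data. The study is a pilot with mainly descriptive analysis, and these outcomes are secondary.

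Most of this stands, and it rules out two stronger readings:

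- A reader might infer that objective (b) largely lacks follow-up data because the Caffeine Problems Survey is marked once. The documents do not support this. They do not make that survey the outcome, and other measures recur.
- A reader might also infer that people who entered for frequent urination, one of the entry problems ("sleep problems, anxiety or nervousness, frequent urination, heartburn or other digestive issues", or feeling dependent on caffeine), have nothing on which to improve. Urination is an entry option and not a stated outcome, and intake is collected from everyone. Whether any repeated instrument asks about it depends on the separate Measures document, which was not available.

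None of the reply reaches objective (c). Follow-up measures after treatment cannot replace an untreated value, and the plan expressly promises the comparison for all secondary outcomes.

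**Conclusion.** The point holds for objective (c). As scheduled, the randomised comparison on caffeine-related problems cannot be computed, because none of the ten repeated problem or symptom scales is taken at the delayed group's untreated 7-week visit. The comparison on caffeine intake is unaffected. For objective (b), only the treatment-visit baseline is missing, and change from screening to Weeks 7 and 14 remains available. The weekly wording conflicts with Table 1, but this is a reconciliation of text with limited analytic consequence. The primary feasibility and acceptability outcome is not touched.

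This rests on Table 1 as extracted from the PDF. A column shift is possible, since the observer row also disagrees with the text. The gap at Treatment does not depend on the table alone, because the text for that visit lists only intake, and no shift turns a single mark for the Caffeine Problems Survey into repeated measurement. The Measures document could define further weekly content, although the text refers to Table 1 for it.

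**What to change.** 1. In Table 1 and in the Treatment Televisit text of section 4.a, add the problem measures used for objectives (b) and (c): the Caffeine Use Disorder Questionnaire, GAD-7, PSQ-I, Insomnia Severity Index, GSRS and the PROMIS forms. Add the Caffeine Problems Survey if it is meant as an outcome. They should be completed before the manual is given. The delayed group is the minimum. Doing it in both groups would also supply the treatment-visit baseline in section 7.b.
2. State which instrument defines caffeine-related problems as an outcome, and make sure it is marked at Week 7 and Week 14.
3. Reconcile the weekly wording with Table 1, either by marking a caffeine-problem measure in the weekly column or by removing the phrase.

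Adding only the Caffeine Problems Survey, or only the two caffeine-specific instruments, would leave the anxiety, sleep and gastrointestinal comparisons in objective (c) without a control value.

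The cost is an edit to the schedule and some questionnaire minutes at a visit planned for under 30 minutes, with no new instrument. The plan's own estimates suggest that this fits: the Week 7 televisit already carries all the measures listed by name in item 1, plus the intake and acceptability surveys, within the same limit, and the manual briefing generally takes under five minutes.
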